2. LIST OF ABBREVIATIONS

See Medicine Glossary:

Term	Definition / description
ACE	Angiotensin Converting Enzyme
AE	Adverse Event
AESI	Adverse Event of Special Interest
AHR	Aryl Hydrocarbon Receptor
ALT	Alanine Aminotransferase
AST	Aspartate Aminotransferase
AUC	Area under the Plasma Concentration Curve
AUC $0-\infty$	Area under the Plasma Concentration Curve from 0 to ∞
AUC t_1-t_2	Area under the Plasma Concentration Curve from t_1 to t_2
AUC t_1-t_2,ss	Area under the Plasma Concentration Curve from t_1 to t_2 at steady state
BI	Boehringer Ingelheim
BMI	Body Mass Index
CKD	Chronic Kidney Disease
CKD-EPI	Chronic Kidney Disease-Epidemiology Collaboration
C _{max}	Maximum Plasma Concentration
C _{max,ss}	Maximum Plasma Concentration at steady state
C _{pre,ss}	Pre-dose Plasma Concentration at steady state
CS	Corticosteroid
ECG	Electrocardiogram
ECGPCS	Electrocardiogram Pharmacokinetic Concentration Analysis Set
eCRF	Electronic Case Report Form
EDC	Electronic Data Capture

Boehringer Ingelheim
TRIAL STATISTICAL ANALYSIS PLAN
1434-0004

Page 6 of 41

228892_1168295_1.0

Proprietary confidential information © 2024 Boehringer Ingelheim International GmbH or one or more of its affiliated companies.

eGFR	Estimated Glomerular Filtration Rate
EoS	End of Study (corresponds with End of Trial)
EoT	End of Treatment
ES	Entered Set
ESKD	End Stage Kidney Disease
FAS	Full Analysis Set
FDA	Food and Drug Administration
FSGS	Focal Segmental Glomerulosclerosis
FUP1	Follow-up Visit #1
GCP	Good Clinical Practice
gCV	Geometric Coefficient of Variation
GGT	Gamma-Glutamyl Transferase
gMean	Geometric Mean
HA	Health Authority
IB	Investigator's Brochure
ICE	Intercurrent Event
ICF	Informed Consent Form
ICH	International Council on Harmonisation
IgA	Immunoglobulin A
IRT	Interactive Response Technology
MedDRA	Medical Dictionary for Drug Regulatory Activities
[name]
PD	Pharmacodynamics
PK	Pharmacokinetics
PPS	Per Protocol Analysis Set
QT	Time between start of the Q-wave and end of the T-wave in an electrocardiogram
QTc QT	interval corrected for heart rate
QTcF QT	interval corrected for heart rate using the method of Fridericia

**Boehringer Ingelheim
TRIAL STATISTICAL ANALYSIS PLAN
1434-0004**

Page 7 of 41

228892_1168295_1.0

Proprietary confidential information © 2024 Boehringer Ingelheim International GmbH or one or more of its affiliated companies.

RPM	Report Planning Meeting
SAE	Serious Adverse Event
SGLT2	Sodium-Glucose Cotransporter-2
SOP	Standard Operating Procedure
SRC	Safety Review Committee
TS	Treated set
TSAP	Trial Statistical Analysis Plan
TPE	Total Protein Excretion
TRPC6	Transient Receptor Potential Cation subfamily C Member 6
ULN	Upper Level of Normal
UPCR	Urine Protein-Creatinine Ratio

3. INTRODUCTION

As per ICH E9 (1), the purpose of this document is to provide a more technical and detailed elaboration of the principal features of the analysis described in the protocol, and to include detailed procedures for executing the statistical analysis of the primary and secondary variables and other data.

This Trial Statistical Analysis Plan (TSAP) assumes familiarity with the Clinical Trial Protocol (CTP) version 5.0 (Dated 08Jan24), including any Protocol Amendment(s). In particular, this TSAP is based on the planned analysis specification as written in CTP Section 7.2. Therefore, TSAP readers may consult the CTP for more background information on the study, e.g., on study objectives, study design and population, treatments, definition of measurements and variables, planning of sample size, randomization.”

SAS® Version 9.4 (or later) will be used for statistical analyses. R version 4.0.2 (or later) with “DoseFinding” package [R15-2001] will be used for analysis based on MCP-Mod.

4. CHANGES IN THE PLANNED ANALYSIS OF THE STUDY

2) Two additional analysis sets were added to the list of Analysis Sets.

- The Per Protocol Analysis Set (PPS), consisting of all patients who were randomized and completed treatment with evaluable measurements of primary endpoint at both baseline and end of treatment visits within the residual period (5 days), has been included in the set of Analysis Sets analyzed in the trial.
The PPS is the analysis set used in the Sensitivity analysis.
- The Electrocardiogram Pharmacokinetic Concentration Analysis Set (ECGPCS) has also been added. This patient set includes all subjects from the Treated Set who provided at least one pair of a valid drug plasma concentration and a corresponding (i.e. time-matched) ECG endpoint to be used in the exposure-response analysis e.g. concentration-QT plots. For placebo subjects, the plasma concentration is set to zero and hence always considered as valid. The decision whether a time deviation between PK blood sampling and ECG recording is acceptable (and thus whether the pair of values were used) will be made no later than at the Report Planning Meeting (RPM) before database lock.

3) The CTP stated, as part of the primary analysis, that an ANOVA model, for the proteinuria (24-hr urine protein-creatinine ratio (UPCR)) change from baseline at week 12 (and other endpoints, as applicable), would be used to see the difference(s) across arms. However, an ANCOVA model with use of corticosteroid (CS) at randomization and baseline 24-hr UPCR, as covariates will be utilized instead. This

change was performed to align with the protocol study design that stratifies by CS use at randomization to ensure even distribution of patients taking CS across treatment groups, and to further control for any potential confounding effects related to CS use. Therefore, ensuring a more robust analysis.

5. ENDPOINT(S)

5.1 PRIMARY ENDPOINT(S)

Primary endpoint will be used as described in, the CTP, Section 5.1.1: The primary endpoint is patients achieving at least 25% reduction in UPCR from 24-hour urine (24-hr UPCR) relative to baseline after 12 weeks of treatment. The baseline UPCR will be from the average of two 24-hour urine samples collected before Visit 2.

5.2 SECONDARY ENDPOINT(S)

5.2.1 Key secondary endpoint(s)

This section is not applicable as there are no key secondary endpoints specified in the CTP.

5.2.2 Secondary endpoint(s)

[figure not shown]
Secondary endpoint(s) will be used as described in the CTP, Section 2.1.3 and assessments described in CTP, Section 5.1.1.

[figure not shown]
The secondary endpoints are:

Secondary endpoints are listed in CTP Section 2.1.3 and will be assessed, as follows:

- Change in 24-hr UPCR relative to visit 3 at week 12: the samples will be from the 24-hour urine samples collected at visits 3 and 12.
- Change in 24-hr UPCR relative to baseline at week 13: the samples will be the 24-hour urine samples collected at baseline and week 13.
- Change in 24-hour urinary protein excretion relative to baseline at week 12.
- The following pharmacokinetic parameters of BI 764198 will be determined, if feasible:
 - Steady state trough concentration $C_{pre,ss}$ on week 4 and week 12

For details on efficacy assessments and definition of baseline, see CTP Section 5.1.1.

6. GENERAL ANALYSIS DEFINITIONS

6.1 TREATMENT(S)

Refer to Section 4 of the CTP for details.

6.2 IMPORTANT PROTOCOL DEVIATIONS

A protocol deviation (PD) is important if it affects the rights or safety of the study subjects, or if it can potentially influence the primary outcome measurement(s) in a non-negligible way. Patients with important PDs that could potentially impact the evaluation of the primary endpoint(s) will be excluded from PPS, if applicable.

Handling of iPDs in analysis is included in the DV domain specifications and stored within the TMF in EDMS. Important PDs will be reviewed at Clinical Quality Monitoring Process (CQMP) conducted periodically during the trial.

6.3 INTERCURRENT EVENTS

An intercurrent event (ICE) is defined as an event of early discontinuation, lost to follow-up, or death.

The strategies for handling intercurrent events in this trial are as follows:

- Hypothetical estimand: assuming all subjects remained adherent to the assigned trial medication and the study protocol. This strategy will include all data collected until time of an ICE.
- Treatment policy estimand: using all available data including data collected after an ICE.

6.4 SUBJECT SETS ANALYSED

Subject sets will be used, as defined in the CTP Section 7.2.1.

The following analysis sets will be defined for statistical analyses:

- Entered Set (ES): This patient set includes all patients who signed informed consent. The ES will be used for the analysis of patient disposition.
- Randomized Set (RS): This patient set includes all patients who signed the informed consent form and were also randomised, regardless whether the patient was treated with trial medication or not.
- Treated Set (TS): This patient set includes all patients who received at least one dose of trial medication. The TS is used for safety and treatment exposure.
- Full Analysis Set (FAS): This patient set includes all patients who were randomized and treated with evaluable measurements of 24-hr UPCR at baseline and at least one 24-hr UPCR measurement after the first dose. The FAS is the main analysis set for the analysis of efficacy.
- Per Protocol (PPS): All patients who were randomized and completed treatment with evaluable measurements of primary endpoint at both baseline and end of treatment visits within the residual period (5 days). The PPS is the analysis set used in the Sensitivity analysis.
- Pharmacokinetic Analysis Set (PKS): This patient set includes all patients in the TS who provide at least one PK endpoint that was not excluded due to protocol violation relevant to the evaluation of PK or due to PK non-evaluability.
- ECG Pharmacokinetic Concentration Set (ECGPCS): This patient set includes all subjects from the TS who provided at least one pair of a valid drug plasma concentration and a corresponding (i.e. time-matched) ECG endpoint to be used in the exposure-response analysis e.g. concentration-QT plots. For placebo subjects, the plasma concentration is set to zero and hence always considered as valid. The decision whether a time deviation between PK blood sampling and ECG recording is acceptable (and thus whether the pair of values were used) will be made no later than at the RPM before database lock.

If a patient receives incorrect medication for the entire treatment period, efficacy will be analysed as randomized and safety will be analysed as treated. If a patient receives incorrect medication for part of the treatment period, the primary analysis of the primary efficacy endpoint will be performed on the randomized set following the intention-to-treat principle. Such cases will be discussed in the RPM, if needed.

Table 6.4: 1 Subject sets analysed

Class of analysis	Subject sets						
	ES	RS	TS	FAS	PPS	PKS	ECGPCS
Efficacy				X	X		
Safety & treatment exposure			X				
Demographic & baseline		X					
Disposition	X						
Pharmacokinetic					X		
Exposure-Response						X	

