14. Two separate 24-hour urine samples will be collected on separate days prior to visit 2. The 24-hour urine samples should be collected only after confirmation that the patient met all the eligibility criteria for the trial, and the collections should be close to visit 2 as much as possible. Visit 2 must be rescheduled if UPCR data is not available at least from one 24-hour urine sample.
15. One 24-hour urine sample should be collected before visit 3. For information and collection time points, see section [6.1](#).
16. One 24-hour urine sample should be collected before EoT visit. EoT visit must be rescheduled if the 24-hour urine sample is not collected for UPCR measurements. For information and collection time points, see section 6.1.
17. One 24-hour urine sample will be collected before FUP1. For information and collection time points, see section 6.1.

20. One blood sample for pharmacogenomics will be taken at visit 2. If the sample is not collected at visit 2, it can be collected at a later visit.
21. Refer to Table [10.1: 1](#) for planned PK sampling schedule. The date and exact time of trial medication administration will be recorded in the eCRF together with the date and exact time when PK samples are drawn.
22. An additional PK sample will be collected at the FUP1 visit.
23. Randomization will be performed using the IRT Platform at least a week before the scheduled visit 2 date. Randomization call must occur only after patient eligibility (including UPCR criteria, eye exams) has been confirmed and UPCR data from central lab is available from at least one 24-hour urine sample during screening period. Trial medication will be shipped directly to the patient via a courier from a central depot unless not permitted by local/site regulations. First dose will be administered at visit 2. A telephone call (video call if possible) from site to patient should occur in about 24 hours (or next working day) after the site receives the delivery notification from the courier. For more information, see section [4.1.4](#).

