For visits 3, EoT, and FUP1, one 24-hour urine sample will be collected. Collection should start preferably the day before the respective study visit and end on the day of the visit.

Visit 2 must be rescheduled if at least one of the 24-hour urine sample is not collected. The EoT visit must be rescheduled if the 24-hour urine sample is not collected before the visit. Visits must be rescheduled as soon as possible.

For patients participating in the trial remotely via the DCT model, urine collection containers for all the study visits will be sent to the patient's home, and the urine samples will be shipped to the study site via a courier. If patients live close to the study site, they may also pick up the urine collection containers from the study site and bring the 24-hour urine samples to the study site.

If possible, patients should be reminded (e.g. via telephone) during the screening period and ahead of the applicable visits to collect the 24-hour urine samples.

Collection of 24-hour urine samples may be repeated for logistical reasons (e.g. samples lost or patient could not complete the 24-hour collection) or technical issues (e.g. sample not fit for analysis).

Pregnancy tests

All WOCBP will undergo serum pregnancy test at the screening visit (visit 1). Patients who test positive for the serum pregnancy test will be excluded from the trial. If the patient is a WOCBP, the status of the menstrual cycle should be assessed before the administration of the first dose of trial medication (visit 2): in case of a delayed or missed period, the PI should use their clinical judgement and the results of the pregnancy test at visit 2 to assess the participants pregnancy status and confirm eligibility before intake of trial drug.

Urine pregnancy tests will be done at all study visits starting from visit 2 (except visit 3 and phone visits). If the urine pregnancy test is positive, trial medication will be stopped and a serum pregnancy test will be performed to confirm pregnancy. If the serum pregnancy test is positive, the patient will be discontinued from the trial. EoT visit will be scheduled as soon as possible, and patient should complete the EoS visit. If serum pregnancy is negative, patient may continue in the trial and resume treatment with trial medication. If the urine pregnancy

Clinical Trial Protocol

Proprietary confidential information © 2025 Boehringer Ingelheim International GmbH or one or more of its affiliated companies

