7.2 PLANNED ANALYSES

7.2.1 General considerations

The following analysis sets will be defined for statistical analyses:

- Entered Set (ES): This patient set includes all patients who signed informed consent. The ES will be used for the analysis of patient disposition.
- Randomized Set (RS): This patient set includes all patients who signed the informed consent form and were also randomized, regardless whether the patient was treated with trial medication or not.
- Treated Set (TS): This patient set includes all patients who received at least one dose of trial medication. The TS is used for safety analyses as well as demographics and baseline characteristics.
- Full Analysis Set (FAS): This patient set includes all patients who were randomized and treated with evaluable measurements UPCR at baseline and at least one UPCR measurement after first dose. The FAS is the main analysis set for the analysis of efficacy.
- Pharmacokinetic Analysis Set (PKS): This patient set includes all patients in the TS who provide at least one PK endpoint that was not excluded due to protocol violation relevant to the evaluation of PK or due to PK non-evaluability.

For the analysis of efficacy, patients will be analyzed as randomized, without regard to any treatment changes.

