6.6 HANDLING OF MISSING DATA AND OUTLIERS

No missing data will be imputed in the UPCR, [REDACTED], and urinary protein excretion analyses. Handling of missing PK data will be performed according to the relevant Corporate Procedure.

Missing or incomplete AE dates will be imputed according to BI standards (4). With respect to safety evaluations, it is not planned to impute missing values.

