7.4 PRIMARY OBJECTIVE ANALYSIS

7.4.1 Primary analysis of the primary endpoint(s)

This is an exploratory trial. No confirmatory testing is performed and hence neither null nor alternative hypotheses are defined. Nominal p-values may be presented. The FAS will be used for the analysis of the primary endpoint.

An exploratory analysis for the primary endpoint, in terms of proportion of patients achieving at least 25% UPCR reduction relative to baseline at week 12 (patients missing the week 12, 24-hr UPCR will be counted as non-responders) will be conducted by providing 95% confidence intervals from each treatment group, via logistic regression utilizing corticosteroid use at randomization (variable CORTIC) and baseline 24-hr UPCR, as covariates. The baseline UPCR will be from the average of two 24-hour urine samples collected before visit 2 (before the first dose). Graphical representations of change in 24-hour UPCR from baseline will also be presented.

The primary estimand of interest is the treatment effect, assuming all subjects remained adherent to the assigned trial medication, and the study protocol using a hypothetical approach, i.e., study drug is taken as directed. This analysis will include all data collected until time of an ICE. For primary analysis, UPCR measurements after ICE will not be included. ICE and the strategies for handling intercurrent events are defined in the CTP section 7.2.2 and [section 6.3](#), above, as follows:

An intercurrent event (ICE) is defined as an event of,

[figure not shown]
- Early discontinuation,
- Lost to follow-up, or
- Death.

The strategies for handling intercurrent events in this trial are as follows:

- (1) Hypothetical estimand: assuming all subjects remained adherent to the assigned trial medication and the study protocol. This strategy will include all data collected until time of an ICE.
- (2) Treatment policy estimand: using all available data including data collected after an ICE.

For this analysis only the Hypothetical estimand will be considered.

In addition, an analysis of covariance (ANCOVA) model (for the UPCR change from baseline at week 12) will be used to see differences across arms, with corticosteroid use at randomization and baseline 24-hr UPCR, as covariates. Dose-response relationship based on reduction in log of UPCR may be explored using a graphical approach.

[figure not shown]

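### The FAS drops treated patients with no post-dose 24-hour urine, so they escape the plan's own rule that a missing week-12 value counts as non-response

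*SAP*

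**What the plan says.** **Who is in the FAS.** SAP 6.4 requires patients to be randomised and "treated with evaluable measurements of 24-hr UPCR at baseline and at least one 24-hr UPCR measurement after the first dose". Protocol 7.2.1 likewise asks for "at least one UPCR measurement after first dose". Neither text says that the qualifying urine must be taken on treatment or before an intercurrent event.

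**How the primary endpoint is analysed.** SAP 7.4.1 says "The FAS will be used for the analysis of the primary endpoint", and in the same section that "patients missing the week 12, 24-hr UPCR will be counted as non-responders". It adds: "For primary analysis, UPCR measurements after ICE will not be included". SAP 7 bases percentages on every subject in the set, with or without a value, so FAS membership is the responder denominator. SAP 6.6 says in general terms "No missing data will be imputed in the UPCR"; I take the specific non-responder rule in 7.4.1 to govern the responder endpoint.

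**When urine is collected.** Protocol 6.1 and Flow Chart A schedule post-dose 24-hour urines at visit 3 (day 4), EoT (week 12) and FUP1 (week 13). Early stoppers should have the EoT procedures as soon as possible and then FUP1. Protocol 6.1 adds a safeguard: "The EoT visit must be rescheduled if the 24-hour urine sample is not collected before the visit". Visit 3 and FUP1 have no such rule.

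**Baseline.** Flow Chart A, footnote 23, allows randomisation only once "UPCR data from central lab is available from at least one 24-hour urine sample during screening period".

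**The concern.** The non-responder rule is there so that patients without a week-12 value stay in the analysis. The FAS condition removes those with the least information before that rule can reach them. Whether an early stopper counts as a failure or disappears then depends on handing in a urine container after randomisation, not on treatment assigned or received.

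The dividing line is also odd. A stopper can enter the FAS solely through an early EoT or FUP1 urine taken after the intercurrent event, and the primary analysis then discards that value. The urine changes the denominator and nothing else.

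At stake are the reported responder proportions and their 95% intervals in a trial of 15 per arm. Each arm's rate can only be raised by such exclusions. The trial is exploratory with no confirmatory testing, so no type I error rate is involved.

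**Working it through.** **1. Two patients side by side.** Both are randomised, dosed, have a baseline 24-hour UPCR and no week-12 value.

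- Patient A gave one post-dose 24-hour urine (day 4, early EoT or FUP1). A is in the FAS and counts as a non-responder.
- Patient B gave none, for example after early loss to follow-up, death or withdrawal of consent. B is outside the FAS and not counted. Rescheduling EoT cannot recover such a patient.

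**2. Effect on one arm's rate.** With x responders among n patients, removing one non-responder changes the rate by x/(n-1) - x/n = x/[n(n-1)]. Starting from n = 15 (protocol 7.5):

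| Responders | none dropped (/15) | 1 dropped (/14) | 2 dropped (/13) | 3 dropped (/12) |
|---|---|---|---|---|
| 4 | 26.7% | 28.6% | 30.8% | 33.3% |
| 5 | 33.3% | 35.7% | 38.5% | 41.7% |
| 6 | 40.0% | 42.9% | 46.2% | 50.0% |

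Each step is 1.9 to 3.8 points. For a placebo arm with 2 responders, the first step is 2/(15×14) = 1.0 point.

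**3. Effect on the difference.** Take 5/15 on a dose and 2/15 on placebo, a difference of 20.0 points. The counts are illustrative.

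- One or two dropped on drug only: 5/14 - 2/15 = 22.4 points; 5/13 - 2/15 = 25.1 points.
- Two dropped on drug, one on placebo: 5/13 - 2/14 = 24.2 points.
- One or two dropped on placebo only: 5/15 - 2/14 = 19.0 points; 5/15 - 2/13 = 17.9 points.
- Equal losses of one or two: 3/14 = 21.4 points; 3/13 = 23.1 points.

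**4. Chance of exceeding the 25-point goal in protocol 7.5.** The inputs there are response rates of 40%, 30% and 20% on the doses, 9% on placebo and 15 per arm. The protocol gives 73.4%. Exact enumeration of independent binomials with a shared placebo arm gives 80.7%, so I do not reproduce it. Simplifications the protocol does not state come near it (placebo fixed at 9%: 72.7%; 13 evaluable per arm: 72.2%). I do not call it an error here, and the present point does not depend on it.

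The documents give no dropout rate, so I assumed 1 to 3 stoppers per affected arm, none with a post-dose urine, and applied the protocol's rates to the patients with week-12 data. Dropped is the current rule; kept means counted as non-responders.

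| Stoppers in | 1: dropped / kept | 2: dropped / kept | 3: dropped / kept |
|---|---|---|---|
| 80 mg only | 77.2% / 77.2% | 79.5% / 73.5% | 78.7% / 69.6% |
| all three doses, not placebo | 75.1% / 75.1% | 78.0% / 68.3% | 77.9% / 60.5% |
| all four arms equally | 76.8% / 76.8% | 72.2% / 72.2% | 66.7% / 66.7% |

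If each patient instead drops out at random at the same rate in every arm, and none of the dropouts has a post-dose urine, dropped versus kept is 78.2% v 77.8% at 5% dropout, 76.7% v 74.5% at 10% and 75.8% v 66.7% at 20%. These are upper bounds, since most dropouts should have at least one urine.

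**The case against.** **The affected group is small.** A treated patient must miss all three scheduled urines despite the early EoT visit and its rescheduling rule. This stands, and it limits the size of the problem.

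**The fix conflicts with the estimand.** The primary estimand is hypothetical (everyone adherent), and scoring an unobserved patient as a failure does not estimate that. As a comment on the plan this is fair. But SAP 7.4.1 already scores missing week-12 values as failures under that estimand. The change only applies the same rule to every treated patient.

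**Some of the plan is redacted.** Protocol 7.2.3.1 and 7.2.3.2 foresee sensitivity analyses and a treatment-policy analysis, and a treated-set analysis may exist in text we cannot see. That would not alter the visible FAS definition or its use for the primary analysis.

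**Stronger readings do not hold.** A reader might infer that the day-4 sample alone decides inclusion. It does not, because any 24-hour UPCR after first dose qualifies. A reader might also infer a bias in favour of the drug, since the stopping rules include QT prolongation, which the protocol reports as dose-dependent. But the visit 3 urine is collected before that visit, so a patient stopped for a finding at visit 3 or later would normally already qualify. A patient stopped earlier should still have the EoT and FUP1 urines. Nothing shows that giving no urine at all is dose-related. Finally, the 25.1-point result above requires two losses at 80 mg and none on placebo; one placebo loss brings it to 24.2. The 25-point goal appears only in the sample-size section and is not a decision rule in SAP 7.4.1.

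**Conclusion.** The two rules conflict in the text, and the denominator of the primary responder analysis depends on post-randomisation urine collection. With 15 per arm and 4 to 6 responders, each exclusion raises that arm's rate by about 2 to 4 points, and by less in an arm with few responders. The shift is modest beside the sampling error: the exact 95% interval for 6/15 is 16.3% to 67.7%.

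The direction for the drug-placebo comparison is not determined. It favours the drug if losses fall on active arms and works against it if they fall on placebo. With equal numbers lost, the chance of passing 25 points is unchanged and the observed difference moves little. These sizes rest on raw proportions, not the covariate-adjusted logistic estimates, and on assumed numbers of stoppers. It is worth correcting because the remedy is nearly free, not because a large bias has been shown.

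**What to change.** In SAP 6.4, define the FAS for the responder analysis as all randomised patients who took at least one dose of trial medication and have a baseline 24-hour UPCR, and delete the post-dose UPCR condition. Record this in SAP section 4 as a change from the protocol before unblinding, and align protocol 7.2.1 at its next amendment. The ANCOVA continues to use patients with a week-12 value.

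The change is feasible. Randomisation already requires a central-laboratory 24-hour UPCR, and SAP 6.7 averages two baseline samples only if both are available, so every correctly randomised and dosed patient should qualify. Both logistic covariates, corticosteroid use and baseline UPCR, are known before dosing.

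If the present FAS is kept, the SAP should state whether a urine taken after the intercurrent event qualifies a patient, and the report should give the number of treated patients outside the FAS by arm, with reasons.

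The cost is one sentence in each document. Each arm's responder rate can only stay the same or fall slightly; the difference from placebo may move either way.
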